11 STATISTICAL CONSIDERATIONS

11.1 Study Hypothesis

The primary objective of this study is to determine the relationship between DHA exposures following IV dosing and markers of physiologic dysfunction associated with severe malaria. This objective can be framed as a series of statistical hypothesis tests, each evaluating the effect of the DHA exposure parameter on the marker of physiologic dysfunction, measured at a specific timepoint, while adjusting for covariates. The null hypothesis is that there is no effect of exposure on response, and the alternative hypothesis is that there is an effect. The secondary objectives can be framed in an analogous manner, with time to hospital discharge and measures of parasite clearance as the response variables.

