5. SAMPLE SIZE CONSIDERATIONS

A maximum of 100 participants will be enrolled in the study. This maximum of 100 participants would provide sufficient sample size to achieve precision on PK parameters following the FDA pediatric precision criteria for conducting PK studies (achieving a 95% confidence interval (CI) within 60% and 140% of the geometric mean).

Simulations in R version 3.4.2 were used to explore power to detect simple linear relationships between exposure and response in the analysis of the primary objective with the planned sample size. The primary objective of this study is to determine the relationship between DHA exposures after IV dosing and markers of physiologic dysfunction associated with severe malaria. This objective can be framed as a series of statistical hypothesis tests, each evaluating the effect of the DHA exposure parameter on the marker of physiologic dysfunction measured at a specific timepoint, adjusting for covariates. The null hypothesis is that there is no effect of exposure on response, and the alternative hypothesis is that there is an effect.

Because the primary objective of this study encompasses multiple exposure and response variables, and the response variables are measured at multiple timepoints, there are multiple exposure-response relationships that are of interest (one for each unique combination of exposure variable, response variable, and timepoint). Thus, there is a need to control type I error. As this study is exploratory (hypothesis-generating) rather than confirmatory, Benjamini-Hochberg procedure is used to control the false discovery rate at 0.05 [Table 5].

For a multiple hypothesis test, average power is defined as the proportion of false null hypotheses correctly rejected [6]. Table 3 provides the average power computed from 5000 simulations, varying the following quantities:

- Number of total statistical tests, representing the number of combinations of exposure variable, response variable, and timepoint to be tested in support of the primary objective
- Value of R^2 for the true, non-null exposure-response relationships
- Proportion of tests with true, non-null exposure-response relationships with the specified R^2
- Sample size

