## Mean and Standard Deviation of EC50, for example ##
mean(fit_param$ec50)
sd(fit_param$ec50)
```

Exploratory scatterplots for the response outcome measure at each timepoint given the exposure measure will be utilized to assess whether a log-transformation of the response variable may be necessary. These exploratory scatterplots as well as goodness of fit diagnostic plots will be used to assess reasonableness of model assumptions. If Emax model assumptions seem unlikely to hold, linear or polynomial models will be considered as informed by the exploratory scatterplots.

A linear model for primary outcome effect, E_i , is defined as follows:

$$E_i = E_{0,i} + \beta P_i + \eta^T X_i + e_i,$$

where E_i represents the given response outcome measure for the i th participant at the given timepoint, $E_{0,i}$ is the baseline response outcome measure for participant i , P_i is the exposure parameter value for participant i , X_i are the values of the additional covariates included in the model, and e_i are the measurement errors for participant i . These measurement errors are assumed to be independent and normally distributed with mean zero and nonzero variance. In addition to the covariates listed in Section 6.4, actual time of response measurement post-first dose will also be considered for inclusion in the model.

If linear models are fit for a primary outcome effect, the following pseudocode will be used for model fitting and to extract p-values for the exposure model parameter.

```
/* Linear model fit and output p-values */
proc glm data=dataset(where=(population=p and response=r));
*catvar = any categorical covariates included in the model;
*refvalues = the value(s) to be used as the reference level for categorical
covariate(s);
class catvar(ref=refvalues);
*baseresp = response at baseline;
*othercovars = any other covariates (including those specified in the class statement)
included in the model;
model resp = baseresp exposure othercovars / noint ss3;
by timepoint;
ods output ModelAnova=tests3;
run;
data tests3; set tests3(where=(source='EXPOSURE')) ;
rename ProbF=pval;
run;
```

A polynomial model for primary outcome effect, E_i , is defined as follows:

$$E_i = E_{0,i} + \sum_{j=1}^a \beta_j P_i^j + \eta^T X_i + e_i,$$

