where E_i represents the given response outcome measure for the i th participant at the given timepoint, $E_{0,i}$ is the baseline response outcome measure for participant i , P_i is the exposure parameter value for participant i , a is the highest order exponent included in the model with its selection informed by exploratory data plots, X_i are the values of the additional covariates included in the model, and e_i are the measurement errors for participant i . These measurement errors are assumed to be independent and normally distributed with mean zero and nonzero variance. Again, in addition to the covariates listed in Section 6.4, actual time of response measurement post-first dose will also be considered for inclusion in the model. Estimated log-likelihood statistics or other model fit statistics may be used to assist in covariate selection for linear or polynomial models.

If linear models are fit for a primary outcome effect, the following pseudocode will be used for model fitting and to extract p-values for the exposure model parameter.

```
/* Polynomial model fit and output p-values */
data dataset; set dataset;
```

```

*exposure^j from 2 up to a will be calculated;
exposurea=exposure**a;
exposurea_1=exposure** (a-1);...
run;
proc glm data=dataset(where=(population=p and response=r));
*catvar = any categorical covariates included in the model;
*refvalues = the value(s) to be used as the reference level for categorical
covariate(s);
class catvar(ref=refvalues);
*exposure... exposurea: exposure raised to the powers 1 up to a will be included as
covariates in the model;
*baseresp = response at baseline;
*othercovars = any other covariates (including those specified in the class statement)
included in the model;
model resp = baseresp exposure... exposurea othercovars / noint ss3;
by timepoint;
ods output ModelAnova=tests3;
run;
data tests3; set tests3(where=(source='exposurea'));
rename ProbF=pval;
run;

```

Model assumptions, including normality of participant-specific measurement errors, will be assessed via exploratory scatterplots and residual plots, which will also inform whether a log-transformation of the response variable may be necessary. In the event that model assumptions are not met, additional models or transformations of the response variables will be assessed, and any changes from the analyses described in this SAP will be fully described in the interim CSR.

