Models fit for the sensitivity analysis of the primary analysis using the subset of the PD Analysis Population who did not receive IV artesunate or other artemisinin-based therapy before enrollment will be of the same form as those fit in the primary analysis for the respective PD response variable, exposure parameter, and timepoint. Covariates included in each model fit for this sensitivity analysis will be those included in the respective primary analysis model with effects that remain estimable in the sensitivity analysis subset. The type of model, covariates included, and any transformations applied to the response outcome measure for each final primary analysis model will be presented in [Table 19](#) by marker of physiological dysfunction, PK exposure parameter, and timepoint for the PD Analysis Population and the subset of the PD Analysis Population that did not receive IV artesunate or other artemisinin-based therapy before enrollment.

For each model fit, the relationship between the response outcome measure at the given timepoint and the exposure measure will be assessed via a hypothesis test. If an Emax model is fit for the response outcome measure and exposure parameter, the following null hypothesis will be tested:

$$H_0: EC_{50} = 0.$$

Post-hoc distributional assessments will be performed for EC_{50} , and EC_{50} will be transformed if necessary to have an approximately normal distribution for inference. Possible transformations may include log-transformations. Point estimates and CIs for EC_{50} will be presented after their transformation back to their original scale. If any transformation is applied for the EC_{50} , the transformation will be presented in [Table 19](#).

Otherwise, if a linear model is fit for the response outcome measure and exposure parameter, the following null hypothesis will be tested:

$$H_0: \beta = 0.$$

Furthermore, if a polynomial model is fit for the response outcome measure and exposure parameter, then the following null hypothesis will be tested:

$$H_0: \beta_a = 0.$$

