To adjust for multiple testing, the set of p-values for the exposure effect parameters, which correspond to tests of the effect of exposure on response at each timepoint, will be adjusted using the Benjamini-Hochberg procedure to preserve the false discovery rate for the primary outcome at 0.05 in both the primary analysis and the sensitivity analysis of the primary outcome measures. The corresponding point estimates of the parameters being tested will be presented with 95% CIs and p-values for each marker of physiological dysfunction and exposure parameter in [Table 17](#) for participants in the PD Analysis Population and in [Table 18](#) for the subset of the PD Analysis Population with no IV artesunate or other artemisinin-based therapy before enrollment. Significant p-values after the Benjamini-Hochberg procedure has been performed will be indicated.

Individual trend plots for each marker of physiological dysfunction over time will be presented by sex and weight group beginning in [Figure 24](#) and continuing through [Figure 34](#). Graphical displays of each marker of physiological dysfunction by exposure will be presented by planned timepoint beginning in [Figure 35](#) and continuing through [Figure 210](#) for participants in the PD Analysis population and in the subset of the PD Analysis Population that did not receive any IV artesunate or other artemisinin-based therapy before enrollment. These figures will show individual measurements alongside model estimates.

Individual listings of BCS assessments will be presented in [Listing 11](#). Individual listings of temperature are included in [Listing 20](#). Individual listings of biochemistry and hematology markers of physiological dysfunction are given in [Listing 17](#) and [Listing 18](#), respectively. Individual listings of exposure parameters by weight group will be presented in [Listing 13](#).

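### Where a polynomial is fitted, the primary test uses only the highest-power coefficient, which does not test whether exposure has an effect

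*SAP*

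**What the plan says.** **The null.** Protocol Section 11.1: "The null hypothesis is that there is no effect of exposure on response". SAP Section 5 gives the same null with its alternative: "The null hypothesis is that there is no effect of exposure on response, and the alternative hypothesis is that there is an effect". SAP Section 8.1 says that, for each fitted model, "the relationship between the response outcome measure at the given timepoint and the exposure measure will be assessed via a hypothesis test".

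**The model.** For continuous markers an Emax model comes first. "If Emax model assumptions seem unlikely to hold, linear or polynomial models will be considered as informed by the exploratory scatterplots". A polynomial contains every power of exposure from 1 to a, and a "is the highest order exponent included in the model with its selection informed by exploratory data plots". Section 8.1 also lets fit statistics help with covariate selection in linear and polynomial models.

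**The test.** Linear cells test the slope. For the rest, "if a polynomial model is fit for the response outcome measure and exposure parameter, then the following null hypothesis will be tested", namely β_a = 0. The code agrees: the step beginning "data tests3; set tests3(where=(source='exposurea" keeps only the row for the top power. The implementation note and footnote a of Table 17 confirm that only this coefficient, its interval and its p-value are tabulated. What enters the BH adjustment is described as "the set of p-values for the exposure effect parameters, which correspond to tests of the effect of exposure on response at each timepoint".

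**What is absent.** No joint test of the exposure terms appears anywhere in the SAP, and Section 15 (changes in planned analyses) neither lists nor justifies the choice. Figures 35 to 210 show the full fitted models, but no p-value for exposure as a whole is planned.

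**The constant.** The linear and polynomial PROC GLM statements in Section 8.1 both carry the NOINT option.

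**The concern.** In a polynomial of order a, the stated null is β_1 = … = β_a = 0. That null implies β_a = 0, but β_a = 0 does not imply the null: a strong straight-line effect inside a quadratic fit has β_2 = 0. The SAP's test answers whether the curve needs its last term, and the result is then labelled as the answer to whether exposure matters.

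The error runs in one direction. For a fixed order and a model with a constant, the test of β_a keeps its level, and a rejection does imply an exposure effect. The harm is in the non-rejections: a real effect can appear in Tables 17 and 18 as not significant. The power in SAP Table 3 was simulated for simple linear relationships. It is not wrong, but it does not carry over to polynomial cells tested this way.

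**Working it through.** **Inputs from SAP Section 5 and Table 3.** N = 75; 11 markers × 4 exposure parameters × 4 timepoints = 176 tests; R² = 0.2; 5% non-null (0.05 × 176 = 8.8, taken as 9); false discovery rate 0.05.

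**Assumptions not in the documents.** Independent tests, no covariates in steps 1 to 3, the exposure distributions and true shapes named below, and three stand-in rules for choosing line or quadratic, because the SAP gives no numerical rule.

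**Step 0: the plan's own figure.** Simple linear regression with a two-sided slope test and BH gives average power 0.851 (Table 3: 0.85). At N = 90 it gives 0.929 (Table 3: 0.93).

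**The two tests.** Let RSS_k be the residual sum of squares with powers 1 to k and a constant.
- SAP rule: F = (RSS_{a−1} − RSS_a) / [RSS_a/(N − a − 1)], on 1 and N − a − 1 df.
- Joint test: F = [(RSS_0 − RSS_a)/a] / [RSS_a/(N − a − 1)], on a and N − a − 1 df.

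For a = 2 and N = 75, the denominator df is 72.

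**Step 1: bounds.** A quadratic is fitted in every cell; exposure is normal.

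| Share of signal that is quadratic | SAP rule | Joint test |
|---|---|---|
| 0% (linear truth; worst case) | 0.00 | 0.75 |
| 25% | 0.08 | 0.71 |
| 50% | 0.33 | 0.69 |
| 100% | 0.74 | 0.68 |

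**Step 2: after choosing line or quadratic.** Exposure is lognormal with CV 50%, and Emax is not offered. Entries are average power over all non-null cells, SAP rule vs joint test. Losses in points, in brackets, are from unrounded values.

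| Truth | Quadratic if AIC lower | If curvature p < 0.05 | If curvature p < 0.01 |
|---|---|---|---|
| Linear | 0.68 vs 0.83 (15) | 0.78 vs 0.83 (4) | 0.82 vs 0.82 (<1) |
| Saturating | 0.34–0.43 vs 0.80–0.83 (39–46) | 0.52–0.61 vs 0.80–0.83 (21–28) | 0.69–0.75 vs 0.78–0.81 (6–9) |
| U-shape | 0.40 vs 0.41 | 0.40 vs 0.41 | 0.43 vs 0.40 |

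The saturating truths have EC50 at 0.5 or 1 times the median exposure. Over exposure CV 30% to 80%, the losses under the three rules are 14–15, 4–5 and 0–1 points (linear) and 27–50, 12–35 and 3–15 points (saturating). For the U-shape they run from −6 to +9.

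**Step 3: affected cells only.** At CV 50% the quadratic is picked in 16%, 5% and 1% of linear-truth cells, 45–57%, 25–34% and 10–15% of saturating cells, and 93%, 83% and 64% of U-shaped cells. Share of those cells flagged after BH, SAP rule vs joint test:

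| Truth | AIC | p < 0.05 | p < 0.01 |
|---|---|---|---|
| Linear | 0.01 vs 0.85 | 0.05 vs 0.91 | 0.25 vs 0.97 |
| Saturating | 0.07–0.08 vs 0.84–0.86 | 0.13–0.16 vs 0.91–0.92 | 0.38–0.42 vs 0.97–0.98 |
| U-shape | 0.42 vs 0.43 | 0.47 vs 0.48 | 0.63 vs 0.59 |

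A strict rule makes affected cells rare, but a linear or saturating effect in such a cell is still mostly missed.

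**Step 4: NOINT, as a separate check.** There is no exposure effect, N = 75, exposure CV 50%, no other covariate, and a baseline-to-follow-up correlation of 0.3 to 0.95. The marker means (SDs) are assumed. Entries are false rejection at nominal 5%.

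| Marker, baseline to follow-up | Linear slope | β_a | Joint |
|---|---|---|---|
| Temperature 38.5 (1.0) to 37.0 (0.6) °C | 7% | 10–14% | 10–12% |
| Haemoglobin 7.5 (2.0) to 7.0 (1.8) g/dL | 18–67% | 25–89% | 30–95% |
| Creatinine 50 (20) to 40 (15) µmol/L | 40–90% | 41–93% | 59–99% |
| Lactate 4.0 (2.5) to 2.0 (1.0) mmol/L | 94–100% | 81–95% | 99–100% |

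With an intercept or a class covariate, the rates are 4–6%. With measurement time as the only added covariate they are 4–11% when time varies little (CV 5%), up to 43% at CV 20% and up to 93% at CV 50%.

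**The case against.** The SAP tries Emax first, so a saturating truth, where the loss is largest, is the case meant to leave the polynomial branch. This bears on size. With a Hill-1 Emax model also competing by AIC (itself an assumption), the quadratic is picked in 26–28% of saturating cells, against 47–59% in the same run without it. The saturating losses in step 2 are therefore upper-side figures. The forced quadratic on a linear truth is only a bound, because the SAP has a linear branch. For a U-shape, a natural reason to choose a polynomial, little changes.

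The study calls itself exploratory. Table 17 says which coefficient it shows, Table 19 lists the powers used, and the figures print the whole fit. A careful reader could therefore see the curve, but would still have no valid p-value for it, and the BH flag would still be mislabelled.

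NOINT is a distinct defect that acts in the opposite direction, towards false positives. SAP Section 8 expects adjustment for some of several categorical covariates, and any one entered as a class variable restores the constant. The sample equations under Figures 35 to 38 also print a constant. That suggests an intercept is intended, but the code does not ensure one, and the Table 19 note allows a model with exposure alone. NOINT does not enlarge the main point, but the joint test needs a constant to be valid.

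None of this makes β_a = 0 equivalent to the stated null.

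**Conclusion.** The concern holds. Formula, code, table note and footnote all agree on a test that does not match the stated hypothesis in polynomial cells, and this should be corrected before the analysis.

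The logic is certain; the size is not. It depends on how many cells end up polynomial (possibly none), on how linear or polynomial is chosen, and on the true shape. At N = 75 and exposure CV 50%, with Emax left out, the loss of average power is under 1 to 15 points for a linear truth and 6 to 46 for a saturating truth, and about nil for a U-shape. Inside an affected cell with a linear or saturating truth, the SAP rule flags 1% to 42% of real effects, against 84% to 98% for the joint test. The NOINT false-rejection rates rest on assumed marker values and apply only when no class covariate is in the model.

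**What to change.** In SAP Section 8.1, replace H0: β_a = 0 with H0: β_1 = … = β_a = 0. Test it by the F test on a numerator degrees of freedom, using a multi-row CONTRAST in PROC GLM or a comparison of the models with and without exposure terms. Enter that p-value in BH in both the primary and the sensitivity analysis. In Tables 17 and 18, label it as the joint test and refer to the fitted curve in Figures 35 to 210; a contrast between the 25th and 75th percentiles of exposure is optional. Remove NOINT from the linear and the polynomial code.

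The cost is SAP wording, one CONTRAST statement, two code edits and a changed footnote, with no new data. Some power is lost when the signal is purely top-order: 0.74 to 0.68 at N = 75 (6 points) and 0.85 to 0.80 at N = 90 (5 points).

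The joint test does not cure choosing the order from the same data. With no true effect, nominal 5% becomes 9.2% (SAP rule) vs 7.6% (joint) under AIC, 9.8% vs 7.3% under p < 0.05, and 6.0% for both under p < 0.01. Fixing the order, or a rule for choosing it, in advance would address that.

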8.2. Secondary Pharmacodynamics Analyses

8.2.1. Time to Hospital Discharge

We will perform secondary PD analyses to assess the relationship between measures of DHA exposure, including AUC_{0-12} , C_{max} , $t_{1/2}$ and T_{max} , and time to first hospital discharge. We will utilize Cox proportional hazards regression models for time to first hospital discharge and each DHA exposure parameter. Covariate selection (see Section 6.4 for a list of covariates that will be considered) for these models will be aided by exploratory boxplots of time to first hospital discharge by covariate, presented in [Figure 211](#) for participants in the PD Analysis Population.

The Cox proportional hazards regression model for time to hospital discharge and AUC_{0-12} , for example, would have cumulative hazard function

$$\Lambda(T_{HD} | AUC_{0-12,i}, X_i) = \lambda(T_{HD}) \times \exp\{\beta AUC_{0-12,i} + \eta^T X_i\},$$

where T_{HD} represents time to hospital discharge, $\lambda(T_{HD})$ is the baseline hazard function, X_i are the additional covariates included in the model, β is the expected change in the log hazard ratio relative to a one unit change in AUC_{0-12} holding the other covariates constant, and η is the vector of expected changes in the log hazard ratio comparing levels of the included covariates holding AUC_{0-12} and other covariates constant. The Cox

proportional cumulative hazard function for time to first hospital discharge and C_{\max} , $t_{1/2}$, or T_{\max} would be of the same form.

Models fit for the sensitivity analysis of the secondary analysis for time to hospital discharge using the subset of the PD Analysis Population who did not receive IV artesunate or other artemisinin-based therapy before enrollment will be of the same form as those fit in the secondary analysis for time to hospital discharge and the respective exposure parameter. Covariates included in each model fit for this sensitivity analysis will be those included in the respective secondary analysis model with effects that remain estimable in the sensitivity analysis subset. The type of model and covariates included for each analysis model will be presented in [Table 22](#) by PK exposure parameter for the PD Analysis Population and the subset of the PD Analysis Population that did not receive IV artesunate or other artemisinin-based therapy before enrollment.

Summary statistics, including mean, SD, median, minimum, and maximum, for time to hospital discharge will be presented in [Table 20](#). Hazard ratios for time to hospital discharge corresponding to a one-unit change in exposure parameters adjusted for other covariates included in the models will be presented with corresponding 95% confidence intervals in [Table 21](#). Forest plots of hazard ratios and 95% CIs by exposure parameter will be presented for time to hospital discharge in [Figure 215](#).

The following pseudocode will be used to fit a Cox proportional hazard model for time to hospital discharge and estimate the hazard ratio for a one-unit increase in exposure along with its Wald confidence interval after adjusting for other covariates.

```
/* Fit Cox PH Model and Estimate Hazard Ratio for Exposure Parameter */
proc phreg data=dataset(where=(population=p));
*catvars = any categorical covariates included in the model;
*refvalues = the value(s) to be used as the reference level for categorical
covariate(s);
class catvars(ref=refvalues);
*othercovars = any other covariates (including those specified in the class statement)
included in the model;
model dischtime * censoringvar(1) = exposure othercovars / ties=breslow;
by timepoint;
hazardratio exposure / cl=wald;
ods output hazardratios = hrest;
run;
```

